5.8. Analysis of Safety Data

The summary of safety and tolerance will be performed for all patients in SAF.

The safety analysis will be based on the reported AEs, clinical laboratory evaluations, physical examination, vital signs, and 12-lead ECG.

Thresholds for treatment-emergent Potentially Clinically Significant Values (PCSV) in laboratory variables, vital signs and ECG are defined in [Appendix 10.3](#). The baseline when determining treatment-emergent PCSV refers to the baseline value of current study.

The time interval to detect any event or abnormality is between the first injection of study medication and EOS.

Subgroups are defined by key baseline factors recorded on the CRF and listed to be considered for safety analyses:

- Age group (≥ 18 - <40 , ≥ 40 - <65 , ≥ 65)
- Sex (Male, Female)
- Ethnicity: Hispanic or Latino (no/yes)
- Race (White, Black or African American, Asian, Other)
- Duration of AD based on data from parent studies (< 26 years, ≥ 26 years)
- Baseline weight group (<70 kg, ≥ 70 - <100 kg, ≥ 100 kg)

5.8.1. Adverse Events

Listings of TEAEs, serious TEAEs, TEAEs resulting in death and study drug discontinuation will be generated.

Number and proportions of patients reporting TEAEs will be summarized for the following TEAEs, sorted by the decreasing frequency of SOC, HLT and PT:

- TEAEs
 - TEAEs by SOC/PT
 - TEAEs by SOC/HLT/PT
 - TEAEs by PT
 - Common TEAEs by SOC/HLT/PT (incidence with HLT $\geq 5\%$)
 - Common TEAEs by SOC/HLT/PT (incidence with PT $\geq 5\%$)
 - TEAEs by severity by SOC/PT
 - Severe TEAEs by SOC/PT
 - TEAEs related to study medication as assessed by the investigator by SOC/PT

- Severe TEAEs related to study medication as assessed by the investigator by SOC/PT
- Serious TEAEs by SOC/PT
 - Serious TEAEs by SOC/PT
 - Serious TEAEs by SOC/HLT/PT
 - Serious TEAEs related to study medication as assessed by the investigator by SOC/PT
- TEAEs leading to permanent discontinuation of study treatment by SOC/PT
- Death by SOC/PT

In addition, the number of events per 100 patient-year (NEPY) and number of patients with at least one event per 100 patient-years (EAIR) will be calculated and summarized for the following:

- TEAEs by SOC and PT
- Severe TEAEs by SOC/PT
- TEAEs related to study medication as assessed by the investigator by SOC/PT
- Severe TEAEs related to study medication as assessed by the investigator by SOC/PT
- Serious TEAEs by SOC/PT
- TEAEs leading to permanent discontinuation of study treatment by SOC/PT
- AESI by AESI category and HLT/PT

These calculations will be adjusted for the duration of the TEAE period. The detailed methodology of NEPY and EAIR is described in [Appendix 10.5](#).

5.8.2. Clinical Laboratory Measurements

Laboratory measurements include clinical chemistry, hematology and urinalysis results, and will be converted to standard international units. Summaries of laboratory variables will include:

- Descriptive statistics of laboratory result and change from baseline by visit
- The number (n) and percentage (%) of patients with abnormal lab value during study whose screening and baseline values are normal (overall and per each lab parameter)
- The number (n) and percentage (%) of patients with treatment-emergent PCSVs during study, depending on data
- Shift tables based on baseline normal/abnormal and other tabular and graphical methods may be used to present the results for parameters of interest

Listing of all laboratory parameters normal range, abnormal flag and treatment-emergent PCSV by subject and visit will be provided.

The graph of mean change and/or percentage change from baseline value for lab parameters by visit will be provided.

5.8.3. Analysis of Vital Signs

Summaries of vital sign variables will include:

- Descriptive statistics of vital sign variable and change from baseline by visit
- The number (n) and percentage (%) of patients with treatment-emergent PCSV, depending on data
- Shift tables based on baseline normal/abnormal and other tabular and graphical methods may be used to present the results for parameters of interest

Listings will be provided with flags indicating the treatment-emergent PCSVs, depending on data.

5.8.4. Physical Exams

The number (n) and percentage (%) of patients with abnormal physical exams will be summarized at the scheduled visits. A summary of treatment-emergent abnormal findings will be provided.

5.8.5. Analysis of 12-Lead ECG

Summaries of 12-lead ECG parameters will include:

- Each ECG parameter and change from baseline
- The number (n) and percentage (%) of patients with PCSV, depending on data
- ECG status (i.e. normal, abnormal) summarized by a shift table

Listings will be provided with flags indicating PCSVs, depending on data.

5.8.6. Analysis of Ophthalmological Examination

For those patients enrolled in the optional ophthalmology sub study, the ophthalmology exam data will be included as a subset of the safety analysis set. Patients in the safety analysis set who enrolled in the ophthalmology sub-study will be categorized into subgroups based on whether or not they had an existing ophthalmological AE at the time of sub-study entry.

- No ophthalmological AE
- At least one ophthalmological AE
 - Ended prior to sub-study entry
 - Ongoing at sub-study entry

Summary of ophthalmological exam data will be performed for all patients in the safety analysis set who enrolled in the ophthalmology sub-study and by the above defined subgroups (i.e. ophthalmological AE or not at the sub-study entry) using descriptive statistics and will include:

- Summary of patient disposition
- Summary of demographic and baseline characteristics of current study
- Summary of past ocular history
- Summary of past and current treatment of ophthalmology
- Summary of concomitant medications and procedures taken during the ophthalmology sub-study
- Summary of Treatment Emergent Ophthalmology Adverse Events (TEAE) Onset during the Ophthalmology Sub-study (i.e. between the informed consent date of sub-study up to the last visit of sub-study) by SOC/PT
- Summary of Ophthalmic Adverse Event Assessment
- Summary of Ophthalmological Examination and Procedures
- Summary of observed intraocular pressure and its change from baseline at the beginning of sub-study
- Slit lamp biomicroscopy, shift table for normal/abnormal status for each test
- Indirect ophthalmoscopy shift table for normal/abnormal status for each test

5.9. Analysis of Pharmacokinetic Data

For this study, sampling will be sparse and the types of analyses will be:

- Descriptive statistics at each sampling time

No formal statistical analysis will be performed within the scope of this plan. For the descriptive statistical analysis, concentrations below the lower limit of quantitation (LLOQ) will be set to zero.

5.10. Analysis of ADA Data

5.10.1. Analysis of ADA Data

The ADA variables described in Section 4.8 will be summarized using descriptive statistics in the ADA analysis set. Frequency tables of the proportion of patients with pre-existing immunoreactivity, treatment-emergent, treatment-boostered, persistent ADA responses, and titer categories will be presented as absolute occurrence (n) and percent of patients (%).

- Pre-existing immunoreactivity is defined as either an ADA positive response in the assay at baseline of parent study with all ADA results negative post first dose of the current study, OR a positive response at baseline of parent study with all ADA results less than 4-fold baseline titer levels of parent study, post first dose of the current study.
- Treatment emergent response is defined as a positive response in the ADA assay post first dose of current study when baseline results of parent study are negative or missing. The treatment emergent responses will be further characterized as Persistent, Indeterminate or Transient
 - Persistent Response – defined as a treatment emergent ADA response with two or more consecutive ADA positive sampling time points separated by greater than (>) 12-week period (greater than 84 days), with no ADA negative samples in between.
 - Indeterminate Response – defined as a treatment-emergent response with only the last collected sample positive in the ADA assay
 - Transient Response - defined as a treatment emergent ADA positive assay response that is not considered persistent or indeterminate.
- Treatment boostered response is defined as a positive response in the ADA assay post first dose that is greater than or equal to 4-fold over baseline titer levels of parent study, when baselines results of parent study are positive.

The baseline used to define ADA status (treatment emergent, pre-existing immunoreactivity, etc) refers to the baseline ADA value in the parent study.

- Titer Values (Titer value category)
 - Low (titer <1,000)
 - Moderate ($1,000 \leq \text{titer} \leq 10,000$)
 - High (titer >10,000)

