### 2.2. Secondary Objective

The secondary objective of the study is to assess the immunogenicity of dupilumab in adult patients with AD, in the context of re-treatment, and to monitor efficacy parameters associated with long-term treatment.

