1.2.2. Secondary Objectives

The secondary objectives of the study are to assess the immunogenicity of dupilumab in adult patients with AD, in the context of re-treatment, and to monitor efficacy parameters associated with long-term treatment.

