3.2. The Pharmacokinetic Analysis Set (PKAS)

The PK analysis set consists of all treated patients who had at least one non-missing drug concentrations result following the first dose of study drug.

3.3. The Anti-Drug Antibody (ADA) Analysis Set (AAS) and Neutralizing Antibody (NAb) Analysis Set (NAS)

The ADA population consists of all treated patients who received any study drug and who had at least one non-missing ADA result after the first dose of the study drug.

The neutralizing antibody (NAb) Analysis Set (NAS) consists of all patients who received any study drug and who had at least one non-missing Nab result or who had all samples negative in the ADA assay after first dose of the study drug.

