- Gender (Male, Female)
- Race (White, Black or African American, Asian, Others)
- Ethnicity: Hispanic or Latino (yes/no)
- Previous usage of ciclosporin (CsA) (Yes, No)
- Previous usage of methotrexate (MTX) (Yes, No)
- Previous usage of Azathioprine (Aza) (Yes, No)
- Previous use of systemic immunosuppressants for AD (Yes, No)
- History of asthma (Yes, No)
- History of nasal polys (Yes, No)
- History of allergic rhinitis (Yes, No)
- History of food allergies (Yes, No)
- Previous treatment of dupilumab in parent study (Yes, No)
 - For patients who received dupilumab in parent study, data from the following two subgroups will also be summarized.
 - Re-treatment (treatment gap > 8 weeks): – Patients who came from the dupilumab arms of parent studies, and if the gap period between the last dupilumab study drug injection in parent study and the first study drug injection in current study is > 8 weeks (greater than 64 days).
 - Continuous treatment (gap ≤ 8 weeks) – patients who came from the dupilumab arms of parent studies, and if the gap period between the last dupilumab study drug injection in parent study and the first study drug injection in current study is ≤ 8 weeks (less than or equal to 64 days).

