5.11.2. Immunogenicity and Treatment Gaps

Associations between ADA (e.g. ADA status, ADA maximum titers, and neutralizing antibody status) and treatment gaps (i.e. ≤ 8 weeks or > 8 weeks) due to patients resuming treatment under protocol amendment 7 or 8 will be explored.

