6.1. Definition of Baseline for Efficacy/Safety Variables

Unless otherwise specified, the baseline assessment for all measurements will be the latest available valid measurement taken prior to the first administration of study drug in the current study. The following rules specify the determination by both date/time information:

1. For the AE, lab (including biomarker), PK and ADA data, both date and time of the measurement will be used to determine baseline by comparing with the first injection date and time.
2. For other data except AE, lab (including biomarker), PK or ADA, only date of the measurement will be used to determine baseline by comparing with the first injection date.

The baseline value of parent study is defined as the baseline value a patient had prior to the first dose in the parent study. For patients who have been screened for a phase 3 study (R668-AD-1334 or R668-AD-1416), but could not be randomized because of randomization closure, the initial baseline value of the parent study will be the last nonmissing value during the screening period in the parent study.

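### The main ADA tables neither separate re-treated patients nor use the Day 1 sample, so immunogenicity on re-treatment is addressed only in part

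*SAP*

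**What the plan says.** Protocol 2.2 sets as a secondary objective "to assess the immunogenicity of dupilumab in adult patients with AD, in the context of re-treatment", and SAP 1.2.2 repeats it. Protocol 1.2.1 explains the interest as re-exposure and a new course of treatment.

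SAP 3.3 puts into the ADA analysis set every treated patient "who had at least one non-missing ADA result after the first dose of the study drug". SAP 5.10.1 tabulates ADA status and titre category over that set, and SAP 5 summarizes data overall. Treatment-emergent means a "positive response in the ADA assay post first dose of current study when baseline results of parent study are negative or missing". The reference is stated explicitly: "The baseline used to define ADA status (treatment emergent, pre-existing immunoreactivity, etc) refers to the baseline ADA value in the parent study".

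Elsewhere the default baseline is the "latest available valid measurement taken prior to the first administration of study drug in the current study" (SAP 6.1), and that section gives a date-and-time rule for finding it for ADA. Visit 2 (Day 1) includes an ADA sample taken before the injection (Protocol 6.2.2.1 and Table 1, footnote f). No ADA status definition uses it.

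SAP 5.7 defines patients with and without prior dupilumab and splits the former into continuous and re-treated by the gap before the extension. It applies these groups to EASI, IGA and pruritus NRS only. SAP 5.11.2 adds that associations of ADA status, maximum titre and neutralizing antibody (NAb) status with treatment gaps of at most 8 weeks, or more, "due to patients resuming treatment under protocol amendment 7 or 8 will be explored".

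**The concern.** A reader will expect the ADA tables to show what happens when dupilumab is started again. The planned figure mixes three populations: first exposure in the extension, uninterrupted use, and a second course after a break. Its value depends on the mix of patients enrolled.

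The label treatment-emergent also covers two different events for patients with earlier dupilumab: antibodies that first appear in the extension, and antibodies acquired in the parent study that are still detectable after extension dosing. Only the first is evidence about the new course. The boosted category is also measured against the parent baseline titre, so it has the same feature.

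**Working it through.** No ADA rate, sample size or precision target is stated, so there is no plan figure to reproduce. The check is a reading of the definitions plus simple arithmetic.

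**1. Classification.** Applying SAP 5.10.1 to four patient types:

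| Parent-study treatment | Parent baseline | OLE Day 1 | After first OLE dose | SAP status | Against Day 1 |
|---|---|---|---|---|---|
| Dupilumab | Negative | Positive | Positive, titre not up 4-fold | Emergent | Carried over |
| Dupilumab | Negative | Negative | Positive | Emergent | New |
| Placebo | Negative | Negative | Positive | Emergent | New, first exposure |
| Any | Missing | Positive | Positive, titre not up 4-fold | Emergent | Already positive |

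All four fall in the same cell. Among patients with a negative or missing parent baseline, every response that is new against Day 1 is also emergent under the SAP rule, and carried-over responses come on top. In this group the SAP count can only equal or exceed the Day 1 count.

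**2. Reach of SAP 5.11.2.** SAP 2.3 gives about 113 patients with the first gap (median about 17 weeks) and about 272 with the second (median about 10 weeks). SAP 2.2 gives 2678 enrolled.

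- 113/2678 = 4.2%; 272/2678 = 10.2%.
- Any gap: from 272 (complete overlap) to 113 + 272 = 385 (none), that is 10.2% to 14.4%. The other 86% to 90% had no such gap.
- Both medians exceed 8 weeks, so at least half of each group did too: about 113/2 = 57 and 272/2 = 136. At least about 136 distinct patients (136/2678 = 5.1%) had a gap over 8 weeks.

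So 5.11.2 has data, though limited precision. With n = 136 and assumed counts, 3 positives (2.2%) give an exact 95% interval of 0.5% to 6.3%, and 7 (5.1%) give 2.1% to 10.3%. It names no reference sample before resumption. With status still set against the parent baseline, it cannot show whether ADA preceded or followed the restart.

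**3. Carry-over, illustration only.** Let c be the share carrying a parent-study response past Day 1, and m the risk of a new response in the rest. Both are assumed at 1% to 5%.

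- Reported rate = c + (1 − c)m.
- c = m = 1%: 0.01 + 0.99 × 0.01 = 2.0%. c = m = 5%: 0.05 + 0.95 × 0.05 = 9.8%.
- Carried-over share = c / [c + (1 − c)m]: 0.01/0.0595 = 17% (c = 1%, m = 5%) to 0.05/0.0595 = 84% (c = 5%, m = 1%).

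**4. Pooling, illustration only.** Assume 6% ADA in re-treated patients and 2% in the others. With re-treated share w, the pooled rate is 6%·w + 2%·(1 − w): 2.4%, 3.2% and 4.0% at w = 10%, 30% and 50%.

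**5. Group boundary.** 8 × 7 = 56 days, whereas SAP 5.7 glosses 8 weeks as 64 days (64/7 = 9.1 weeks). Patients with a gap of 57 to 64 days are classified differently by the two statements. SAP 4.2 categorizes the same gap as at most 8 weeks and more than 13 weeks.

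**The case against.** The parent baseline is a legitimate choice. For prior-dupilumab patients it is the sample that precedes all dupilumab. A Day 1 reference alone would relabel drug-induced antibodies as pre-existing. For parent-study placebo patients both candidate baselines precede dupilumab. This stands, and it is why the parent-baseline status should stay. A reader might infer that this baseline is an error; the documents do not support that.

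Pooling was deliberate. SAP Table 1 records that the naive, re-treated, interrupted and continuous subsets were dropped to avoid confounding from differences between parent studies, of which SAP 2.1 lists 14. This is a good reason not to read group differences causally. It does not rule out a descriptive split, since the same SAP revision adds a prior-dupilumab subgroup for efficacy.

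The ADA plan is also not wholly tied to the parent baseline. Titre categories are absolute, NAb positivity is an assay result, and the protocol synopsis promises listings by patient and time point in which carry-over can be seen case by case. But listings are not a summary of re-treatment immunogenicity.

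Carry-over counts only if it persists to a later sample. Under the current schedule the first routine one after Day 1 is Week 48. The Amendment 6 history shows that samples at Weeks 4 and 12 existed before then. This may limit the effect but does not remove it.

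Finally, the study is descriptive and promises no comparison between groups. That limits the consequence, but the objective itself names re-treatment.

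**Conclusion.** The point holds as a gap in coverage. The main ADA tables do not isolate re-treated patients or use the Day 1 sample, and responses that arose before Day 1 and persist are counted as emergent in this study. The re-treatment objective is addressed only through the exploratory 5.11.2 analysis of within-study gaps, which involve about 10% to 14% of enrolled patients. Parent-to-extension re-exposure is not examined for ADA.

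A reader might infer that the objective cannot be answered at all. That goes too far: 5.11.2 concerns patients who stopped and resumed, with at least about 136 whose gap exceeded 8 weeks, and the objective does not itself define re-treatment as the parent-to-extension gap.

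A reader might also want a figure for the inflation. None is available, because the documents give neither ADA rates nor the number re-treated from parent studies. The illustrations above rest entirely on assumed inputs. What is supported is the direction: upward, for prior-dupilumab patients with a negative or missing parent baseline.

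**What to change.** In SAP 5.10.1:

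- Keep the parent-baseline classification and label it as the lifetime figure.
- Add a second classification against the predose Day 1 sample of the extension: newly positive, or a titre rise of at least 4-fold.
- Present ADA and NAb results descriptively by no prior dupilumab, continuous and re-treated, using the SAP 5.7 groups.
- First reconcile 8 weeks with 64 days in SAP 5.7, and align the gap categories in SAP 4.2.
- Footnote that differences between groups may reflect differences between parent studies.

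The cost is extra columns and one additional derived status. It needs no new data collection, because the visit 2 sample is already scheduled and SAP 6.1 already says how to identify a current-study ADA baseline. SAP 1 allows revision, SAP 7 foresees addenda, and Protocol 9 has the final SAP issued before database lock.

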5.10.2. Analysis of Neutralizing Antibodies (NAb)

The absolute occurrence (n) and percent (%) of treatment-emergent or treatment boostered ADA positive patients that are positive in the NAb assay will be summarized for patients in the NAb analysis set.

5.11. Association of Immunogenicity with Exposure, Safety and Efficacy

5.11.1. Immunogenicity and Exposure

Associations between ADA and systemic exposure to dupilumab may be explored. Plots of dupilumab concentration may be provided for analyzing the potential impact of treatment-emergent, persistent and titer ADA responses (high, moderate or low) on PK.

5.11.2. Immunogenicity and Treatment Gaps

Associations between ADA (e.g. ADA status, ADA maximum titers, and neutralizing antibody status) and treatment gaps (i.e. ≤ 8 weeks or > 8 weeks) due to patients resuming treatment under protocol amendment 7 or 8 will be explored.

5.11.3. Immunogenicity and Safety and Efficacy

Association of ADA with safety events may be explored with a primary focus on the following safety events during the TEAE period:

- Hypersensitivity (SMQ: Hypersensitivity [Narrow])
- Anaphylaxis (SMQ: Anaphylaxis [Narrow])

Association of treatment emergent and persistent ADA responses and impact on selected efficacy endpoints (ie proportion of patients with IGA 0 or 1, proportion of patients with EASI-75, percent change in EASI score) may be explored (e.g. scatter plot or spaghetti plot).

These above mentioned safety and efficacy analyses will be conducted using the following ADA response categories:

- ADA positive patients, that is patients with treatment-emergent or treatment-boosted response
- ADA negative patients, that is patients with pre-existing immunoreactivity or negative in the ADA assay at all time points
- Patients with persistent ADA response,
- NAb positive patients, that is patients who had positive in the NAb assay at any time point analyzed.
- Peak post-baseline titer level in treatment emergent or treatment boosted ADA positive patients:
 - High,
 - Moderate,
 - Low

